4.4 Safety measurements and variables

Table 5 Safety objective and variables

Objective	Variables
To assess the safety and tolerability during 4 weeks treatment with AZD3355 65 mg bid as add-on treatment to a PPI in partial responders to PPI treatment who still experience GERD symptoms	BP, pulse, ECG, physical examination, laboratory variables, AE recording. Data on paresthesiae collected in specific eCRF module. To be used if patients spontaneously report paresthesiae as an AE

The methods for collecting safety data are described below.

4.4.1 Adverse events

4.4.1.1 Definitions

The definitions of AEs, SAEs and other significant adverse events (OAEs) are given below. It is of the utmost importance that all staff involved in the study is familiar with the content of this section. The Principal Investigator is responsible for ensuring this.

Adverse event

An AE is the development of an undesirable medical condition or the deterioration of a pre-existing medical condition following or during exposure to a pharmaceutical product, whether or not considered causally related to the product. An undesirable medical condition can be symptoms (eg, nausea, chest pain), signs (eg, tachycardia, enlarged liver) or the abnormal results of an investigation (eg, laboratory findings, electrocardiogram). In clinical studies, an AE can include an undesirable medical condition occurring at any time, including run-in or washout periods, even if no study treatment has been administered.

Serious adverse event

A SAE is an AE occurring during any study phase (ie, run-in, treatment, washout, follow-up), and at any dose of the investigational product, comparator or placebo, that fulfils one or more of the following criteria:

- results in death
- is immediately life-threatening

- requires in-patient hospitalisation or prolongation of existing hospitalisation
- results in persistent or significant disability or incapacity
- is a congenital abnormality or birth defect
- is an important medical event that may jeopardise the patient or may require medical intervention to prevent one of the outcomes listed above

The causality of SAEs (ie, their relationship to study treatment) will be assessed by the investigators, who in completing the relevant eCRF must answer “yes” or “no” to the question “Do you consider that there is a reasonable possibility that the event may have been caused by any of the following – investigational product – other medication?”. For further guidance on the definition of a SAE and a guide to the interpretation of the causality question, see [Appendix B](#) to the Clinical Study Protocol.

Note that SAEs that could be associated with any study procedure should also be reported. For such events the causal relationship is implied as “yes”.

Other Significant Adverse Events (OAE)

OAEs will be identified by the Global Safety Physician and if applicable also by the Clinical Study Team Physician during the evaluation of safety data for the Clinical Study Report. Significant adverse events of particular clinical importance, other than SAEs and those AEs leading to early discontinuation of the patient from study treatment, will be classified as OAEs. Examples of these are marked haematological and other laboratory abnormalities, and certain events that lead to intervention (other than those already classified as serious), dose reduction or significant additional treatment. For each OAE, a narrative may be written and included in the Clinical Study Report.

4.4.1.2 Recording of adverse events

AEs will be collected from time of first administration of investigational product until the end of the study. SAEs will be collected from the time informed consent is signed through the entire study period.

AE spontaneously reported by the patient and/or in response to an open question “have you had any health problems during the study since the previous visit” from the study personnel or revealed by observation will be recorded during the study visit at the investigational site and at the follow-up visit.

Findings and values related to physical examinations will be defined as AEs if they are considered clinically relevant deteriorations compared with baseline and pre-dose values, as judged by the investigator.

Deterioration in laboratory values, BP and pulse and ECG need not to be recorded as AEs. However, abnormal values that constitute an SAE, or lead to early discontinuation of administration of any investigational product must be reported and recorded as AEs.

Onset, resolution, maximum intensity, early discontinuation due to AE, action taken, outcome, causality and whether it constitutes an SAE or not will be reported in the eCRF for each AE.

The intensity rating is defined as:

- mild (awareness of sign or symptom, but easily tolerated)
- moderate (discomfort sufficient to cause interference with normal activities)
- severe (incapacitating, with inability to perform normal activities)

It is important to distinguish between serious and severe AEs. Severity is a measure of intensity whereas seriousness is defined by the criteria in section 4.4.1.1. An AE of severe intensity need not necessarily be considered serious. For example, nausea that persists for several hours may be considered severe nausea, but not a SAE. On the other hand, a stroke that results in only a limited degree of disability may be considered a mild stroke but would be a SAE.

Any AEs that are unresolved at the patient's last AE assessment in the study (ie, at the follow-up visit) are to be followed up by the investigator for as long as medically indicated, but without further recording in the eCRF. AstraZeneca retains the right to request additional information for any patient with ongoing AE(s)/SAE(s) at the end of the study, if judged necessary.

Should an overdose (accidental or deliberate) occur, it must be reported in accordance with the procedures described in section 9.3, Procedures in case of overdose, regardless of whether the overdose was associated with any symptom or not. All symptoms associated with the overdose should be reported as AEs.

Should a pregnancy occur, it must be reported in accordance with the procedures described in section 9, Procedures in case of pregnancy. Pregnancy in itself is not regarded as an AE unless there is a suspicion that an investigational product may have interfered with the effectiveness of a contraceptive method.

4.4.1.3 Spontaneously report of paresthesiae

If the patient spontaneously reports paresthesiae (defined as “an abnormal touch sensation in the absence of an external stimulus”), a more thorough questioning will be done, asking for frequency, the patients' description of the symptoms, start of symptoms in relation to intake of investigational product, duration of symptoms and level of discomfort. All patients reporting paresthesiae will have a neurological examination by the investigator. Patients experiencing daily paresthesiae for at least 7 consecutive days will be withdrawn from intake of investigational product, be referred to a board certified neurologist for examination and

followed-up after 12-16 days by the investigator (visit 6). A copy of the report from the neurologist must be provided to AstraZeneca.

4.4.1.4 Symptoms of the disease under study (DUS)

Some adverse conditions are regarded as part of the natural history of the disease/procedures under study.

The following symptoms will not be recorded as AEs during treatment with investigational product unless they fulfil the criteria for SAEs or lead to early discontinuation of the investigational product, since these symptoms are measured outcome variables of interest in the study:

- A burning feeling behind the breastbone, pain behind the breastbone, a burning feeling in the centre of the upper stomach, a pain in the centre of the upper stomach, an acid taste in the mouth, unpleasant movement of material upwards from the stomach, burping (gas coming from the stomach through the mouth), hoarseness, cough, difficulty swallowing, a bitter taste in the mouth, stomach contents (liquid or food) moving upwards to the throat or mouth and heartburn.

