Heartburn and regurgitation have been found to be the two typical symptoms of GERD (Vakil et al 2006). Recently performed cognitive interviews and focus groups confirmed the presence and importance of these two symptoms in patients with GERD symptoms despite PPI treatment (Report from Mapi Values). In addition, these two symptoms were improved in study D9120C00011 in patients treated with AZD3355. In patient interviews and focus groups, other symptoms that might be of relevance in the treatment of GERD were found. These additional symptoms have been reported in the literature as associated with GERD in general. However, the relevance of these in partial responders to PPI treatment is not known. Therefore, the additional symptoms have been added to the existing RDQ, to derive a modified RDQ e-diary which will be evaluated for appropriate measurement properties in this study. In addition, a definition of clinically meaningful change and a responder definition will be established for the target patient population, ie partial responders to PPI treatment who still experience GERD symptoms.

Given the negative impact of GERD symptoms on patients' daily lives, it is important not only to measure treatment induced symptom change but also the impact of this change on patients' lives. A review of existing PRO instruments addressing the impact of GERD symptoms was performed to select the most appropriate instrument for the target patient population (Report from PRO Consulting). The findings indicated that the heartburn version of the Quality of Life in Reflux and Dyspepsia (QOLRAD) questionnaire was the most appropriate starting point. In order to better fit the target patient population, the symptom descriptions of the QOLRAD were revised based on input from patient interviews and focus groups (Report from Mapi Values), to comprise the modified QOLRAD.

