3.2.2 Risk/benefit and ethical assessment

In total, AZD3355 has been administered to 364 healthy volunteers in 13 studies. The drug has been given as single oral doses in the range of 0.1 mg/kg to 2.5 mg/kg, and as repeated oral doses up to 500 mg and as an intravenous infusion of 0.2 mg/kg. In a recently completed study in patients with GERD symptoms despite PPI treatment, 122 patients were randomised to treatment with AZD3355 65 mg twice daily during 4 weeks (D9120C00011). One patient has reported SAEs during active treatment with AZD3355 65 mg twice daily (headache and hypertension), not considered to be drug related by the investigator. Adverse events have generally been mild to moderate and no specific safety concerns have been raised.

Mild to moderate short lasting paresthesiae without other neurological findings have occurred in some healthy volunteers and study patients, most frequently during the first day of administration. Pre-study medical history will be collected specifically to identify information regarding previous episodes of paresthesiae, and patients with current neurological disorders will be excluded. All patients reporting paresthesiae during the study will undergo neurological examination by the investigator. Patients experiencing paresthesiae for 7 consecutive days meet criteria for discontinuation from study treatment, and will be examined by a board certified neurologist.

A Thorough QT study (D9120C00012) was performed, however, this study failed to exclude an effect of AZD3355 on the prolongation of the QTc interval. Therefore until the potential effect of AZD3355 on the QTc interval has been fully evaluated, digital ECG monitoring (dECG) and additional exclusion criteria, have been included in this clinical study.

Since GABA_B agonists may interfere with the barostatic reflex, hemodynamic effects of a dose of 500 mg AZD3355 have been assessed in a TILT study in healthy volunteers (D912C00021). A single dose of 500 mg was given orally and the head-up tilt was performed at predicted C_{max}. Results showed that subjects have a shorter head-up endurance time when taking AZD3355 as compared to placebo. However, the evaluation thus far does not indicate an effect of AZD3355 on the baroreflex itself but rather indicates signs of peripheral vasodilatation.

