Appendix Date	

Appendix D RDQ - RI - US English

Reflux Disease Questionnaire – RI (RDQ-RI diary)

Bedtime:

Please answer the following questions to help us better understand the symptoms you have been experiencing since waking today (from the time you wake up until the time you go to bed) because of your reflux disease. For each question, please choose the answer that is most appropriate to you.

Since waking today, how would you rate the intensity of a burning feeling behind your breastbone?

Did not have

Very mild

Mild

Moderate

Moderately severe

Severe

Since waking today, how would you rate the intensity of pain behind your breastbone?

Did not have

Very mild

Mild

Moderate

Moderately severe

Severe

Since waking today, how would you rate the intensity of a burning feeling in the center of the upper stomach?

Did not have

Very mild

Mild

Moderate

Moderately severe

Severe

Wording to be used for twice daily symptom assessments between visits 1 and 5.

©AstraZeneca, 2008. All rights reserved.
RDQ – Reflux Inhibition, diary – US-English. Version 1.0.

These questions should not be used, copied or distributed in any form without written permission from AstraZeneca R&D, HEOR, S-431 83 Mölndal, Sweden.

Since waking today, how would you rate the intensity of a pain in the center of the upper stomach?

Did not have

Very mild

Mild

Moderate

Moderately severe

Severe

Since waking today, how would you rate the intensity of an acid taste in your mouth?

Did not have

Very mild

Mild

Moderate

Moderately severe

Severe

Since waking today, how would you rate the intensity of unpleasant movement of material upwards from the stomach?

Did not have

Very mild

Mild

Moderate

Moderately severe

Severe

Since waking today, how would you rate the intensity of burping (gas coming from the stomach through the mouth)?

Did not have

Very mild

Mild

Moderate

Moderately severe

Severe

Wording to be used for twice daily symptom assessments between visits 1 and 5.

©AstraZeneca, 2008. All rights reserved.
RDQ – Reflux Inhibition, diary – US-English. Version 1.0.

These questions should not be used, copied or distributed in any form without written permission from AstraZeneca R&D, HEOR, S-431 83 Mölndal, Sweden.

Since waking today, how would you rate the intensity of hoarseness?

Did not have

Very mild

Mild

Moderate

Moderately severe

Severe

Since waking today, how would you rate the intensity of cough?

Did not have

Very mild

Mild

Moderate

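### Listed reflux symptoms are exempted from AE recording by name while the diary asks only about symptoms due to reflux, so mild non-reflux breastbone pain, hoarseness, cough or difficulty swallowing may be captured in neither (minor, cheap to fix)

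*Protocol*

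**What the plan says.** Section 4.4.1.4 sets the rule: "The following symptoms will not be recorded as AEs during treatment with investigational product unless they fulfil the criteria for SAEs". The same sentence then adds a second exception and gives its reason: "or lead to early discontinuation of the investigational product, since these symptoms are measured outcome variables of interest in the study". The list that follows begins "A burning feeling behind the breastbone, pain behind the breastbone, a burning feeling in the centre of the upper stomach" and ends "hoarseness, cough, difficulty swallowing, a bitter taste in the mouth, stomach contents (liquid or food) moving upwards to the throat or mouth and heartburn". It holds 13 symptoms. The operative sentence depends on seriousness and on discontinuation, but not on cause.

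The instrument that makes these symptoms outcome variables is the e-diary in Appendix D. Its bedtime instruction asks about symptoms experienced "since waking today (from the time you wake up until the time you go to bed) because of your reflux disease". The morning instruction carries the same attribution for the night.

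Section 4.4.1.1 defines an AE independently of any causal relation to the product and names chest pain among its examples. Section 4.4.1.2 collects AEs from the first dose to the end of the study, by spontaneous report, an open question or observation. Table 5 in section 4.4 lists the safety variables: blood pressure, pulse, ECG, physical examination, laboratory variables and AE recording. Diary data are not among them.

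**The concern.** An exemption of this kind is sound when the exempted events are fully recorded elsewhere. Here the stated reason is that the diary measures them, but the diary's instruction narrows what the patient is asked to report and the exemption has no matching limit. A symptom on the list with another cause can fall between the two.

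Safety and tolerability over four weeks is the stated additional objective (section 2.2), and AE recording is one of its listed variables. A non-serious event that belongs to neither record would be missing from the tolerability description. Sites also receive two instructions for one event: section 4.4.1.1 gives chest pain as an AE, and section 4.4.1.4 removes pain behind the breastbone by name.

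**Working it through.** No sample size or error-rate figure is involved, so the check is a comparison of texts.

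1. **Match the exempt list to the diary.** The 13 symptoms in section 4.4.1.4 correspond one for one to the 13 items in Appendix D. The reflux attribution stands in the instruction of both reports (2 of 2). It is not repeated in the individual items.

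2. **Look for another source that asks without reflux attribution.** The GSRS (Appendix F) is the only candidate. It is given at visits 1, 2, 4 and 5.

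| Listed symptoms | Count | GSRS question |
|---|---|---|
| Burning behind the breastbone; heartburn | 2 | Item 2, heartburn |
| Burning and pain in the upper stomach | 2 | Item 1, upper abdominal pain or discomfort |
| Acid taste; bitter taste; upward movement of material; stomach contents rising | 4 | Item 3, acid reflux (approximate for the taste items) |
| Burping | 1 | Item 8, burping |
| Pain behind the breastbone; hoarseness; cough; difficulty swallowing | 4 | None |

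   The sum is 2 + 2 + 4 + 1 + 4 = 13. Nine symptoms have at least approximate cover and four have none. The GSRS cover is itself partial: a one-week recall at visits 4 and 5 reaches about 2 × 7 = 14 of the 28 treatment days, and the GSRS is not a listed safety variable.

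3. **Follow one event through the rules.** Take a randomised patient who coughs for several days on treatment. The cough is not serious, does not lead to stopping the product, and the patient puts it down to something other than reflux.
   - Diary: the instruction asks for reflux symptoms and the item asks about cough. Whether it is entered depends on how the patient reads the two together.
   - AE record: the patient may mention it in reply to the open question in section 4.4.1.2, but section 4.4.1.4 says that it is not recorded.
   - GSRS: no item.

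   Capture is therefore not assured. Even if the cough is entered, the diary holds only an intensity, without the causality, action and outcome fields that section 4.4.1.2 requires for an AE.

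4. **Apply the limits of the rule.** The gap excludes SAEs, events leading to discontinuation, and anything outside treatment with the product, so the follow-up period is not covered by the exemption's wording. It also excludes diagnoses: the list contains symptoms, so a respiratory infection, for instance, remains recordable.

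**The case against.** The strongest reply is that section 4.4.1.4 is already limited to reflux. Its heading refers to symptoms of the disease under study, and its opening sentence speaks of conditions belonging to the natural history of the disease or procedures. On that reading the exemption and the diary have the same scope. This is a fair account of the likely intent, but the operative sentence is categorical and lists symptoms by name. A site that follows it literally would leave out a non-reflux cough. The heading does not tell the investigator to judge cause.

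A second reply is that the diary items themselves are unqualified, so many patients may report any cough. That stands, and it is why capture is described as not assured and not as absent.

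Two stronger readings are tempting. A reader might infer that all 13 symptoms are lost whatever their cause. The protocol does not support that: both exceptions apply, reflux-attributed symptoms are in the diary, and the GSRS asks about upper abdominal pain, heartburn, acid reflux and burping.

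A reader might also connect the exemption of breastbone pain with the earlier thorough QT study, of which section 3.2.2 says "this study failed to exclude an effect of AZD3355 on the prolongation of the QTc interval". That link is weak. QTc is followed directly by triplicate digital ECGs with cardiologist review (section 4.4.3.1), heart disease is an exclusion criterion, and QTcF prolongation has its own discontinuation criterion. The AE wording is not the safeguard for that risk.

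Section 1.1 says of the symptoms added to the RDQ: "However, the relevance of these in partial responders to PPI treatment is not known". This gives only modest support. It concerns their relevance to measurement, the same section says that they are reported in GERD generally, and breastbone pain is an original RDQ item.

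**Conclusion.** The point holds in a narrow form. For four symptoms (breastbone pain, hoarseness, cough and difficulty swallowing), a non-serious, non-discontinuing episode during treatment that is not attributed to reflux is not assured of being in the AE data or in the diary.

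The size of any undercount cannot be estimated. The protocol plans 450 randomised patients (225 per arm) over four weeks, but it gives no event rate for these symptoms and no indication of how patients will read the diary instruction. Nor can a distorted comparison between arms be inferred: the rule is the same in both arms, and section 6 does not describe an AE comparison.

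The conclusion rests on two assumptions: that sites apply the operative sentence as worded, and that at least some patients follow the diary's instruction when answering its items. It is a minor point and a cheap improvement.

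**What to change.** Reconcile sections 4.4.1.1 and 4.4.1.4 with the diary instructions in Appendix D. In section 4.4.1.4, limit the exemption to listed symptoms that the investigator judges to be due to the disease under study, and state that a listed symptom judged not due to reflux is recorded as an AE. The two existing exceptions stay, and the diary wording need not change.

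The cost is one sentence, some additional AE entries, and an attribution judgement made under blinding that will misclassify some episodes. A by-arm table of patients whose diary intensity is new or worse than in Part 1 could accompany the safety summary. It uses existing data, but it is optional and belongs in the analysis plan.

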4.4.1.5 Reporting of serious adverse events

Investigators and other site personnel must inform appropriate AstraZeneca representatives of any SAE that occurs in the course of the study within 1 day (ie, immediately but no later than the end of the next business day) of when he or she becomes aware of it.

SAE information will be entered and submitted into the Clinical Operation On Line (COOL) system on the relevant eCRF modules. An automated email alert will be sent to the designated AstraZeneca representative who will work with the investigator to ensure that all the necessary information is available in COOL within the required time frames. The AstraZeneca representative will notify the appropriate AstraZeneca Patient Safety Data Entry Site through COOL via email that a completed electronic SAE module and relevant information from other appropriate eCRF modules is available in COOL. If COOL is unavailable, the investigator should fax a paper back-up SAE report to the AstraZeneca representative immediately, recognising that the same reporting time frames still apply. The investigator is responsible for completing the eCRF as soon as COOL becomes available again.

Follow-up information on SAEs must also be reported by the investigator within the same time frames.

If follow-up indicates a change in the SAE from serious to fatal or life-threatening, this information needs to be available in COOL within 1 day.

If a non-serious AE becomes serious, this and other relevant follow-up information must also be provided to AstraZeneca within 1 day as described above. For a non-serious AE that become serious but which is not fatal or life-threatening a report should be received within 5 days.

The AstraZeneca representative will work with the investigator to compile all the necessary information and ensure that the appropriate AstraZeneca Patient Safety Data Entry Site receives a report by day 1 for all fatal and life-threatening cases and by day 5 for all other SAEs.

All SAEs have to be reported, whether or not considered causally related to the investigational product or to the study procedure(s). All SAEs will be recorded in the eCRF. The investigator is responsible for informing the Ethics Committee and/or the Regulatory Authority of the SAE as per local requirements.

